2.4.5.5 Analyses of electrocardiogram variables

The summary statistics (including number, mean, median, Q1, Q3, standard deviation, minimum and maximum) of all ECG variables (central reading and changes from baseline) will be calculated for each visit or study assessment (baseline, each postbaseline time point, last on-treatment and/or minimum and maximum value during the treatment-emergent adverse event period) by treatment group. Mean changes from baseline with the corresponding standard error will be plotted over time (at the same time points) in each treatment group.

PCSA will be assessed based on age group at each visit. After subjects turn to be adult, the adult criteria will be applied. The incidence of PCSAs at any time during the treatment-emergent adverse event period will be summarized by treatment group irrespective of the baseline level and/or according to the following baseline status categories:

- Normal/missing.
- Abnormal according to PCSA criterion or criteria.

2.4.5.6 Analysis of Tanner scales

Summary of raw value and change of Tanner scales (including number, mean, median, standard deviation, minimum and maximum) from baseline will be presented for each location (pubic hair and breasts in girls, pubic hair and testes in boys) for each visit by gender and treatment groups. The distribution of number of days to the first Tanner stage increase by 1 point, 2 points, and 3 or more points in each location will be estimated by gender and treatment group using the Kaplan–Meier product limit estimator. The Kaplan-Meier for patients first achieving Tanner Stage 5 in either location during the open-label blind period plot also will be provided by treatment group for each gender.

Shift table for Tanner scales shifted from pre-treatment scales at study consent to post-treatment scales at Week 192/EOT will be summarized by gender and location in each treatment group.

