- h* Including systolic and diastolic blood pressure, heart rate, body temperature, weight and height (Height only at V2 and EOT); patient standing in bare or stocking feet. Height and weight is to be documented in the growth charts –Blood pressure (BP) and heart rate to be measured in both the supine and the standing positions (measures taken 3 minutes after supine and 3 minutes after standing). A sphygmomanometer with a blood pressure cuff appropriate to the patient's arm girth is used.
- i* Tanner stage to be assessed at baseline, every 24 weeks and at EOT for all patients (until complete sexual maturity).
- j* Pancreatic ultrasound must be performed if there are clinical or lab abnormalities suggesting pancreatitis or enzymes elevation  $\geq 3$  x ULN and must be followed up with a computed tomography (CT) with contrast or MRI in case of ultrasound with abnormal pancreatic findings
- k* The following routine parameters will be measured at screening, randomization, Weeks 4, 12, 24, 36, 48, then every 12 weeks and at EOT: Hematology and differential panel (hemoglobin, hematocrit, red blood cell count and red blood cell morphology, mean corpuscular volume, white blood cell count, neutrophils, lymphocytes, monocytes, eosinophils, basophils, platelets); Coagulation panel (prothrombin time, and activated partial thromboplastin time); Complete chemistry panel (glucose, creatinine, blood urea nitrogen (BUN), sodium, potassium, chloride, bicarbonate, magnesium, calcium uric acid, aspartate aminotransferase (AST), alanine aminotransferase (ALT), gamma-glutamyl transpeptidase (GGT), lactate dehydrogenase (LDH), total bilirubin, direct/indirect bilirubin, alkaline phosphatase, inorganic phosphorus, total protein, albumin, globulin, albumin/globulin ratio, triglycerides, cholesterol and creatine phosphokinase (CPK). Pancreatic enzymes (serum amylase and lipase); Urinalysis (pH, ketones, protein, glucose, blood, urobilinogen, bilirubin, microscopic sediment, specific gravity). For pubescent females serum pregnancy test  $\beta$ - Human chorionic gonadotropin; ( $\beta$ -HCG) will be performed at screening, randomization and then every 12 weeks

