- a The open label period starts by the transition visit. It is recommended that there is no time gap between the 2 periods, or as short as possible and if possible less than 2 weeks. In case of start of the open label period at the end of the 96 weeks of the double-blind period, the transition visit will generally coincide with the EOT visit of the double-blind period. Recommended windows: The window for obtaining biological samples at any given visit will be  $\pm 7$  days. All other treatment period assessments should be completed within  $\pm 7$  days of the scheduled visit date relative to the transition visit. Post drug elimination follow-up visits should be  $\pm 7$  days of scheduled visit relative to end of treatment.
- b For a regional or national emergency declared by a governmental agency, contingency measures are included in [Section 17.7](#)
- c End-of-treatment and premature discontinuation visit.
- d For patients discontinuing treatment, 2 post drug elimination follow up visits should be scheduled 2 weeks and 4 weeks after study medication discontinuation and initiation of the drug elimination procedure. When applicable patients who prematurely and permanently discontinue study medication will be asked to continue until the planned end of double-blind period (ie, 96 weeks after randomization)
- e Re-consent before starting open-label period and after confirmed MS relapse and when patients turn adults as per local regulations.
- f During the adverse event reporting process, specific questions about pulmonary symptoms and peripheral neuropathy symptoms will be asked. (Patients will be instructed to alert the treating physician of symptoms suggestive of immunodeficiency)
- g Including systolic and diastolic blood pressure, heart rate, body temperature, weight and height; patient standing in bare or stocking feet. Height and weight is to be documented in the growth charts –Blood pressure (BP) and heart rate to be measured in both the supine and the standing positions (measures taken 3 minutes after supine and 3 minutes after standing). A sphygmomanometer with a blood pressure cuff appropriate to the patient's arm girth is used. Of note, during remote visits, only weight will be collected.
- h Tanner stage to be assessed at every 24 weeks and EOT for all patients (until complete sexual maturity).

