#### ***10.1.3.2 Assessments performed on the clinic visits specified***

- Dispense study medication: Week 8, 12 and every 12 weeks.
- EDSS: Every 24 weeks.

- SDMT: Every 24 weeks.
- Laboratory routine parameters at Weeks 4, 12, 24, 36, 48 then every 12 weeks.
- B-HCG every 12 weeks.
- Immunoglobulins and TSH every 24 weeks.
- Physical examinations: Week 12, then every 12 weeks.
- Tanner Staging at Week 24, 48, 72 (until complete sexual maturity defined by Tanner Stage 5).
- Pre- and post- dose plasma PK sampling: Weeks 2, 3, 4, 8, 12, 24, 36.
- Brain MRI: Weeks 24, 48, 72 and 36 if necessary.
- 12-lead ECG: Baseline and at EOT or premature treatment discontinuation.

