#### **10.1.3.4 Assessments performed on the EOT or premature treatment discontinuation**

Patients who complete the treatment period or who prematurely discontinue should complete EOT procedures including both safety and efficacy assessments. This visit does not need to be performed when the patient switches to the open label period after a confirmed relapse or high MRI activity (as per protocol criteria). Prematurely discontinued patients are encouraged to participate in an early permanent treatment discontinuation (EPTD): they will be followed for safety until they complete 96 weeks from randomization. This includes discontinuation from the open label period, when it occurs within 96 weeks of randomization.

- EDSS.
- SDMT.

- Cognitive Battery Test.
- Brain MRI.
- Adverse event reporting.
- Vital signs.
- Physical examination.
- ECG 12-leads.
- Tanner staging.
- Clinical routine laboratories (including immunoglobulins and TSH).
- Concomitant medication.
- Accountability / compliance.
- Teriflunomide PK sampling.

Post drug elimination process (ie, prescribing Cholestyramine or Activated charcoal and scheduling for two follow up visits) should be initiated.

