2.1.4.6 Tanner scales

The Tanner scale (also known as the Tanner Stages I-V) will be used to define physical measurements of growth and development ((including sexual development and endocrine function), based on external primary and secondary sex characteristics, such as the size of the breasts, genitalia, and development of pubic hair.

Tanner stage will be performed at baseline, every 24 weeks and EOT (until the patient completes sexual maturity (defined by Tanner Stage 5).

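### Tanner staging stops at Stage 5, but SAP 2.4.5.6 has no rule for children no longer staged, so by-visit mean stage runs low and the Week 192/EOT shift table may undercount Stage 5

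*SAP*

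**What the plan says.** The stopping rule appears in several places.

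- SAP 2.1.4.6: "Tanner stage will be performed at baseline, every 24 weeks and EOT (until the patient completes sexual maturity (defined by Tanner Stage 5". SAP Tables 1 and 2 (section 1.4) carry the same limit.
- Protocol 1.2, footnote i: "Tanner stage to be assessed at baseline, every 24 weeks and at EOT for all patients (until complete sexual maturity".
- Protocol 1.4, footnote h, for the open-label period: "Tanner stage to be assessed at every 24 weeks and EOT for all patients (until complete sexual maturity".
- Protocol 10.1.3.2: "Tanner Staging at Week 24, 48, 72 (until complete sexual maturity defined by Tanner Stage 5".

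One list is silent on the limit. Protocol 10.1.3.4, the procedures at double-blind EOT or premature discontinuation, simply includes "Tanner staging".

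The analysis is in SAP 2.4.5.6. For each location (pubic hair and breasts in girls, pubic hair and testes in boys) it plans: "Summary of raw value and change of Tanner scales (including number, mean, median, standard deviation, minimum and maximum) from baseline will be presented", and it does so "for each visit by gender and treatment groups". It adds a "Shift table for Tanner scales shifted from pre-treatment scales at study consent to post-treatment scales at Week 192/EOT". It also plans Kaplan-Meier estimates of time to a first increase of 1, 2, and 3 or more points, and of first reaching Stage 5.

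**The concern.** Assessment ends at the moment the outcome of interest is reached, so whether a value is missing depends on the value itself. The by-visit rows are then computed from whatever was collected. A child who reaches Stage 5 during the double-blind period need never be staged in the open-label period. Later rows therefore describe mainly the children who have not yet matured.

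Tanner staging is the trial's measure of sexual development under the safety objective, and SAP section 3 lists it among the key safety results for the interim open-label report. A reader of the tables would see mean stage that is too low and, depending on how EOT is handled, few children arriving at Stage 5. Neither would reflect development in the trial population.

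**Working it through.** **1. Is there a rule elsewhere for children no longer staged?**

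- SAP 2.5.2 (missing data) covers treatment duration, MS history dates, medication dates, adverse events and laboratory-type abnormalities. It does not mention Tanner.
- SAP 2.5.3 (windows) covers MRI, SDMT, laboratory tests and vital signs.
- SAP 2.5.4 (unscheduled visits) covers MRI, SDMT, laboratory tests and vital signs.
- SAP 2.4.5 lets the endpoint value fall back on the closest value before last dose, but this is written for central laboratory or central-reading parameters. Under Protocol 9.3, Tanner is staged by a local clinician.

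So there is no rule.

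**2. Direction of the error, without numbers.** A child at Stage 5 at a location would score 5, the scale maximum, at every later visit. Dropping only maximum values can only lower mean raw stage. Mean change is different. Losing a child at Stage 5 at baseline removes a zero and raises the mean. Losing a child who progressed to Stage 5 removes a gain and can lower it.

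**3. When it starts.** Children at Stage 5 at baseline are not restaged, so if there are any, the first post-baseline row is already affected. If there are none, everyone is staged at Week 24, and the loss begins at the visit after Stage 5 is first recorded.

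**4. Size, as an illustration.** The documents state no Tanner figure to reproduce and give neither the baseline distribution nor the progression rate. Assumed inputs:

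- Baseline shares at Stages 1 to 5: 20/20/25/20/15%, 10/10/20/30/30% or 5/5/15/30/45%.
- Probability *p* of moving up one stage per 24 weeks: 0.15, 0.25 or 0.35.
- Eight visits, no other dropout, and each child staged up to and including the first visit at Stage 5.

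Hand check at Week 24 for the middle case (30% at Stage 5, *p* = 0.25):

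- Baseline mean, all children: 0.1×1 + 0.1×2 + 0.2×3 + 0.3×4 + 0.3×5 = 3.60.
- Baseline mean, children below Stage 5: (3.60 − 1.50)/0.70 = 3.00.
- Week 24, all children: 3.60 + 0.70×0.25 = 3.775.
- Week 24, children still staged: 3.00 + 0.25 = 3.25.
- The row is 0.525 too low at the first post-baseline visit.

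At Week 192:

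| Stage 5 at baseline | *p* | Still staged | Mean stage: all / collected | Mean change: all / below Stage 5 at baseline / collected | At Stage 5: all / collected |
|---|---|---|---|---|---|
| 15% | 0.15 | 63% | 3.79 / 3.06 | 0.89 / 1.04 / 0.89 | 41% / 5% |
| 15% | 0.25 | 48% | 4.23 / 3.37 | 1.33 / 1.56 / 1.42 | 57% / 11% |
| 15% | 0.35 | 34% | 4.55 / 3.66 | 1.65 / 1.94 / 1.90 | 72% / 18% |
| 30% | 0.15 | 43% | 4.27 / 3.30 | 0.67 / 0.96 / 0.75 | 60% / 7% |
| 30% | 0.25 | 30% | 4.56 / 3.52 | 0.96 / 1.37 / 1.26 | 74% / 13% |
| 30% | 0.35 | 20% | 4.75 / 3.74 | 1.15 / 1.65 / 1.76 | 84% / 20% |
| 45% | 0.15 | 30% | 4.55 / 3.49 | 0.50 / 0.90 / 0.65 | 73% / 9% |
| 45% | 0.25 | 19% | 4.74 / 3.65 | 0.69 / 1.26 / 1.12 | 84% / 15% |
| 45% | 0.35 | 12% | 4.86 / 3.82 | 0.81 / 1.48 / 1.61 | 91% / 21% |

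The change for children below Stage 5 at baseline is the all-children change divided by the share below Stage 5 at baseline, for example 0.96/0.70 = 1.37.

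The collected mean stage is 0.7 to 1.1 too low in every row. The collected mean change is 0.0 to 0.8 too high against all children. Against children below Stage 5 at baseline it runs from about 0.25 too low to 0.13 too high.

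**5. Shift table.** If matured children are not staged at EOT, the Stage 5 column holds only those first recorded at Stage 5 at that visit, which is the last column of the table above. If they are staged at EOT, nothing is lost there.

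**The case against.** The strongest defence is that SAP 2.4.5.6 already answers the main question another way. A first increase and a first Stage 5 are recorded before staging stops, so the Kaplan-Meier analyses are largely sound. The safety summaries are descriptive with no systematic testing, the open-label data are non-controlled and supportive, and the number assessed is shown at each visit, so the attrition is visible. All of this stands. It limits the consequences, but does not correct the means or settle the shift table.

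Four stronger readings are tempting and are not supported.

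- *Mean change is understated.* Take only children at Stage 4 at baseline with *p* = 0.35. True mean change after *k* visits is 1 − 0.65^k: 0.58, 0.82 and 0.97 at Weeks 48, 96 and 192. The collected value stays at 0.35. The arithmetic is right, but this is an extreme case. With mixed baselines the error changes sign and depends on the denominator.
- *Matured children are certainly missing from the shift table.* SAP 2.1.4.6 and Protocol 1.4 footnote h point that way. Protocol 10.1.3.4 lists staging at double-blind EOT without exemption, and a programmer might apply the endpoint fallback in SAP 2.4.5 despite its wording. The outcome is uncertain.
- *The Kaplan-Meier analyses are invalid because they include children who cannot rise 1, 2 or 3 points.* A distribution over all patients is a legitimate description. Restricting the risk sets is mostly a preference.
- *The comparison of the two former arms is distorted.* That would need different maturation or baseline mixes by arm, and the documents give no information on either.

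**Conclusion.** The point holds as a gap in a descriptive safety analysis. Followed as written, SAP 2.4.5.6 gives a mean raw stage that is biased low, and that direction needs no assumption about rates. The sign of the error in mean change is not determined by the documents. The shift table undercounts Stage 5 only if the stop is applied at EOT.

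The sizes in the table rest on assumed baseline mixes, constant progression and no other dropout. They show scale and are not forecasts.

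The statement that every lost value is a 5 assumes that staging stops for a location because that location is at Stage 5, and that Stage 5 does not reverse. The second is implied by the stopping rule. The first is not spelled out: the documents do not say whether one location or both must reach Stage 5. If one is enough, later values at the other location are lost too, and they need not be 5.

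The primary endpoint is not affected.

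**What to change.** In SAP 2.4.5.6, with a matching entry in 2.5.2:

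- Once Stage 5 is recorded at a location, carry 5 forward for that location to all later planned visits and to Week 192/EOT while the child remains in the study. Use an observed value where there is one.
- Report, at each visit and in the shift table, how many values were carried forward.
- Show children at Stage 5 at baseline separately from the change summaries.
- State whether complete maturity means Stage 5 at one location or at both. Leave the other location missing, and counted as such, if staging stopped on one alone.

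Reconcile Protocol 10.1.3.4 with Protocol 1.4 footnote h and SAP 2.1.4.6 on whether matured children are staged at EOT.

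Restricting the Kaplan-Meier risk sets by baseline stage is optional.

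The cost is a few sentences and a short derivation. No new data are needed, and the only assumption is that Stage 5 does not reverse.

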2.4.6 Analyses of pharmacokinetic variables

The summary statistics (including number, mean, standard deviation, geometric mean, coefficient of variation, median, minimum and maximum) of teriflunomide plasma concentrations will be calculated for each visit or study assessment for teriflunomide-treated patients.

If date and/or time of the drug intake and/or sampling are missing, then the concentration will not be taken into account. Where concentration values are below the lower limit of quantification (LLOQ), one-half of the LLOQ will be used at given study visits.

Population pharmacokinetic analysis will be conducted per a separate analysis plan and reported separately.

2.4.7 Analyses of immunogenicity variables

The summary statistics (including number, mean, standard deviation, geometric mean, coefficient of variation, median, minimum and maximum) of serum immunoglobulins concentration (IgG, IgM and IgA) will be provided for each visit or study assessment by treatment group.

Listing will be provided for patients with concomitant vaccine administration.

2.5 DATA HANDLING CONVENTIONS

2.5.1 General conventions

The following formulas will be used for computation of parameters.

Demographic formulas

Age = integer part of (date of consent in the double-blind period– date of birth) / 365.25

BMI (in kg/m²) = weight in kg / (height [in m] x height [in m])

Renal function formulas

Creatinine clearance (CrCl) value for children up to 18 years old will be derived from body length and plasma creatinine (Scr) using the updated Schwartz (Bedside Schwartz) equation:

For children/adolescents: CrCl (mL/min/1.73m²) = 0.413 x (height [cm] / Scr [μmol/L]),
where eGFR (estimated glomerular filtration rate) = mL/min/1.73 m²

Creatinine clearance value for adults will be derived using the equation of Cockcroft and Gault:

For males: $crcl(mL/min) = \frac{(140-age) \times weight (kg)}{0.814 \times creatinine (\mu mol/L)}$

For females: $crcl(mL/min) = \frac{(140-age) \times weight (kg)}{0.814 \times creatinine (\mu mol/L)} \times 0.85$

The last height or weight measurement on or before the visit of the creatinine measurement will be used. The age collected at the visit will be used.

